- Any record of pregnancy or breast feeding at the time of treatment initiation.

Patients with medication errors:

- Prescribed and/or administered > 1 dose per week of dulaglutide (6).
- The number of doses/week will be calculated by measuring the time span between the current prescription and the next one (in weeks) and dividing the number of injections prescribed in the current prescription by this time span. This number of doses/week will be used in the cross sectional study as an attribute of the prescription to assess the occurrence of medication errors as described above.

Patients with off-label use:

- Prescribed dulaglutide with no diagnosis of T2DM as defined above, at the beginning of this list of subgroups of populations.
- Prescribed dulaglutide with a diagnosis of T2DM as defined above and without a record of other ADMs during the 6-month baseline period, i.e. dulaglutide was prescribed as first-line therapy.

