9.7. Data Analysis

9.7.1. General Statistical Considerations

The analysis will be performed per country, on the overall data set of eligible patients and per subpopulations.

Data coming from different databases/countries will not be pooled due to the difference between structure of panels of health care professionals who contribute the data, asynchronicity of databases, heterogeneity in data structure, coding, and prescribing practices. The analysis will be done per year, and will not be cumulative. Thus data coming from different years will not be pooled either.

The statistical analysis will be descriptive including standard univariate analysis; no inferential statistical analyses will be conducted. Continuous variables will be described by the number of available values, mean, standard deviation, median, Q1, Q3, minimum and maximum. Data not available in the databases will be reported as missing. Categorical variables will be described as the total number of available values and relative percentage per subgroup of interest. When relevant, 95% confidence intervals will be calculated for the endpoints.

The statistical analysis will be conducted using the SAS[®] software V9.2 or later on Windows[™] (SAS Institute, North Carolina, USA).

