- Since it will not be possible to distinguish between patients that were appropriately prescribed dulaglutide monotherapy (ie, when diet and exercise alone did not provide adequate glycaemic control and the use of metformin was considered inappropriate due to intolerance or contraindications) and patients who were prescribed monotherapy inappropriately (i.e. did not meet these criteria), the number of patients found to be taking off-label first line dulaglutide will be an overestimate of the number of actual patients taking off label first line dulaglutide.
- Medication errors will be evaluated based on the time span between the first prescription and the next one. In a number of cases the next prescription will not be still captured in the database. These cases will be considered as missing data for the analysis of medication errors. Other sources of bias:
 - **Selection bias:** in some databases (for example, French and German DA) the sample of physicians are representative of the physicians in each country in terms of the stratification factors used to select the panel. However, it is not known whether the physicians who belong to the panel have the same prescription behaviour as the physicians who are not part of the panel, especially those who were invited to take part but refused. Similar considerations can be expressed for physicians who belong for a long time and physicians recently included in the panel. To control these biases as much as possible, the distribution of the strata in each data base will be compared to the distribution of strata of the corresponding physicians' population in the country. This limit does not apply to the Swedish cohorts because of their exhaustiveness.
 - **Misclassification bias:** Misclassification bias can result if study subjects are not categorised correctly with regards to exposure or selected patient characteristics. Since the data bases are fully anonymised, it is impossible to verify the information with source data. This bias cannot be controlled as there is no possibility to check the information in databases. For example, the definition of severe renal failure is based on eGFR. However, this value may not be recorded relevantly in the database. Consequently, there may be false negatives of severe renal failure, that is, those with this condition who are classified as not having the severe renal failure.

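### The medication-error rule has no refill tolerance and sets every patient without a next prescription to missing, so it can count early renewal as error and discard classifiable non-errors

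*Protocol*

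**What the plan says.** Section 9.3 of the protocol defines a patient with a medication error as "Prescribed and/or administered > 1 dose per week of dulaglutide". The rate is obtained as follows: "measuring the time span between the current prescription and the next one (in weeks) and dividing the number of injections prescribed", with that span as the divisor. It is then used "as an attribute of the prescription to assess the occurrence of medication errors as described above".

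Section 9.9.1 describes the interval differently: "Medication errors will be evaluated based on the time span between the first prescription and the next one". It goes on: "In a number of cases the next prescription will not be still captured in the database", and "These cases will be considered as missing data for the analysis of medication errors".

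Section 9.7.1 sets the reporting rule: "Categorical variables will be described as the total number of available values and relative percentage per subgroup of interest". Medication error is named in the primary objective (Section 8) and is one of the nine subgroups analysed (Sections 9.2.3 and 9.7.2). The only sensitivity analysis, in Section 9.7.3, concerns off-label use.

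**The concern.** The rule treats the gap between two prescriptions as if it measured dosing. A patient who injects exactly once a week and does not want to run out must renew on or before the day the supply ends. Every renewal before that day gives a rate above 1, so ordinary early renewal and real overuse fall into the same category.

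The missing-data rule adds a second problem. It treats two kinds of patient alike: those whose data end too soon to tell, and those seen long enough without a renewal for the formula to classify them as non-errors.

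Both the frequency of medication errors and the description of the patients in that subgroup depend on this classification. Section 9.9.1 warns that first-line off-label use will be overestimated, but gives no such warning for medication errors.

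**Working it through.** **No plan figure to reproduce.** The protocol states no expected error proportion, no number of injections per prescription and no refill pattern. Pack size and refill timing below are therefore assumptions.

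**1. Early renewal.** Rate = injections ÷ (days to next prescription ÷ 7).
- 4 injections, renewed at 28 days: 4 ÷ 4 = 1.00, not flagged.
- 4 injections, renewed at 27 days: 4 ÷ 3.857 = 1.04, flagged.
- 12 injections, renewed at 83 days: 12 ÷ 11.857 = 1.01, flagged.

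With fractional weeks, one day early is enough whatever the pack size. Rounding to the nearest week would spare renewals up to 3 days early, but no rounding is stated.

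**2. Illustrative size.** Assume 4-injection packs, no patient taking more than one dose a week, and refill intervals normal and rounded to whole days. An interval of 27 days or less is flagged, so the false-flag rate is Φ((27.5 − mean) ÷ SD).

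| Mean interval | SD 2 d | SD 4 d | SD 7 d |
|---|---|---|---|
| 28 d (on the due day) | 40% | 45% | 47% |
| 30 d (2 days late) | 11% | 27% | 36% |
| 32 d (4 days late) | 1% | 13% | 26% |

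Rounding to the nearest week flags 24 days or less, Φ((24.5 − mean) ÷ SD). At a 28-day mean this still gives 4%, 19% and 31%. With an illustrative 7-day tolerance, 20 days or less is flagged, Φ((20.5 − mean) ÷ SD): 0%, 3% and 14% at a 28-day mean, and at most 9% at 30 or 32 days.

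**3. No next prescription.** If a prescription holds n injections and at least n weeks are observed without another, the rate is at most n ÷ n = 1. Under the protocol's own formula that patient is a non-error. If observation is shorter than n weeks, the status is unknown.

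The wave dates in Section 9.1 and the lags in Sections 9.4.1 and 9.5.2 show that both kinds will occur. Follow-up of a patient initiating on 31 December = extraction date − lag − 31 December:
- Disease Analyzer (1 month to 6 weeks), extraction at the start of the quarter: about 20-22 weeks in wave 1 and 7-9 weeks in waves 2 and 3. This is beyond a 4-injection supply.
- Sweden (6 months): 0-13 weeks in wave 1 across the extraction quarter, none in waves 2 and 3.
- SIDIAP (1 year): none in any wave.

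**4. Effect on the proportion.** Let a fraction m of initiators have no next prescription and in fact be non-errors. Flagged ÷ evaluable exceeds flagged ÷ all initiators by 1 ÷ (1 − m):
- m = 10%: 1 ÷ 0.9 = 1.11
- m = 20%: 1 ÷ 0.8 = 1.25
- m = 30%: 1 ÷ 0.7 = 1.43

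The values of m are assumed.

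**5. Which interval.** Section 9.3 attaches the rate to the current prescription, which could be any. Section 9.9.1 uses only the first prescription and the one after it. The two give different numbers of chances to be flagged.

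**The case against.** The strongest reply is that tolerance and rounding are programming detail, that Section 9.7.5 promises an SAP, and that the study is descriptive. Part of this stands: whole-week rounding would remove the one-day-early case. But the cut-off and the single-interval formula are fixed in the protocol itself, and rounding alone leaves sizeable false-flag rates at a 28-day mean.

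Four further points stand and limit the finding.
- A reader might infer that patients with no next prescription cannot be errors. That holds only for those observed past their supply, and only under this formula. Late-year initiators in databases with long lags are truly unknown. Someone who used more than one dose a week and then stopped would be an error the rule cannot see.
- A reader might infer that the reported proportion is certainly inflated. Section 9.9.1 says specialists outside the general-practice data issue some prescriptions. Unseen prescriptions and late renewals lengthen intervals and hide true errors.
- The denominator effect needs evaluable patients as the base. Section 9.9.1's wording and Section 9.7.1's available values point that way, but neither fixes it. Medication error is a subgroup, not a visible row in Table 9.7.4-1. If the flagged count is reported over all initiators, leaving these patients unflagged inflates nothing.
- If any one of 12 intervals could flag a patient, the table's 11-36% at a 30-day mean would become 74% to over 99% with independent intervals. No section states such a rule. Because the study concerns initiations, the two sections can be read as meaning the first interval, but the wording should say so.

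**Conclusion.** The point holds in limited form. As written, the rule misclassifies once-weekly users who renew early unless whole-week rounding is applied, and even that protects only renewals up to 3 days early. Setting every patient without a captured next prescription to missing also discards some whom the formula can classify.

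The illustrative false-flag rate is 40-47% if refills centre on the due day and 1-36% if they average 2-4 days late. It rests on assumed 4-injection packs and normal refill timing. The 1.11-1.43 inflation rests on an assumed 10-30% of classifiable non-errors and an evaluable-only base. Net bias is probably but not certainly upward. The documents contain no refill distribution, so they do not support a claim that the measure mostly captures early renewal.

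This still needs correcting before extraction. It affects a measure named in the primary objective, no sensitivity analysis covers it, and in several scenarios the error exceeds the ±10 percentage points that Section 9.5.1 plans for the smallest country.

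**What to change.** - **Main analysis.** Compute doses per week from cumulative supply: injections in all captured prescriptions before the last one, divided by the weeks from first to last. Alternatively, apply a pre-specified refill tolerance to the single interval. State the rounding. A cumulative rate may also need a stated margin: three 4-injection prescriptions with the next at day 83 still give 12 ÷ 11.857 = 1.01.
- **Sensitivity analysis.** Report the strict single-interval rule (above 1) alongside it.
- **No next prescription.** Classify as no error a patient followed for at least as many weeks as injections supplied without a renewal. Set to missing only those whose database follow-up is shorter than the supply, decided by length of follow-up and not by whether a renewal was seen.
- **Denominator.** State whether the percentage is over evaluable patients or all initiators, and report the number missing.
- **Consistency.** Reconcile Sections 9.3 and 9.9.1 on which prescription intervals are used, and state how several intervals in one patient combine.
- **Limitations.** Add the likely direction of bias, including the opposing effect of prescriptions outside the database.

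The cost is definition wording and programming on data already to be extracted. The downside is that a tolerance or averaging can miss small or isolated excesses: 4 injections in 2 weeks followed by two 4-week refills average 12 ÷ 10 = 1.2, which a wide margin would not flag. The strict analysis still shows these.

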- Patients having at least 6 months of available continuous history prior to the date of the first dulaglutide prescription.

No exclusion criteria will be applied.

Subgroups of interest:

- Populations of interest:
 - Patients with severe renal failure
 - Patients with hepatic disease
 - Patients with heart failure
 - Patients with severe gastrointestinal disease
 - Children and adolescents <18 years of age
 - Elderly patients ≥ 75 years
 - Pregnant and breastfeeding women
- Medication use:
 - Medication errors
 - Off-label use

Variables:

The following variables will be extracted from databases, whenever available, which will be analysed at the baseline (6-month period prior to dulaglutide initiation) and/or index date (dulaglutide initiation):

- Patients' demographics (age and gender) at baseline
- Relevant comorbidities
- Medical history: disease diagnoses

- Concomitant anti-diabetes medications (ADMs) and other drug exposures
- Average daily dosage of prescriptions
- Prescriptions in combination with other ADMs

Data sources:

The following European EHR databases will be used for the feasibility. A subset of these databases will be then selected for the actual study:

- France: IMS Disease Analyzer (French DA)
- Germany: IMS Disease Analyzer (German DA)
- Spain: The Information System for the Development of Research in Primary Care (SIDIAP)
- Sweden: National Patient Register (NPR) and Swedish Prescribed Drug Register (SPDR)
- United Kingdom: Clinical Practice Research Datalink (CPRD)

Study size:

The first analysis and report will commence once at least 1000 patients initiated with dulaglutide become available in the EHR databases with at least 100 patients in the smallest country. All eligible patients of each selected database will be included in the study. Such a sample size would provide a precision of 3% for the entire sample and a minimum precision of 10% for the country with the smallest sample around an estimated proportion of 50% with 95% confidence intervals.

Data analysis:

The analysis will be performed per country, on the overall data set of eligible patients, 0.75 or 1.5 mg prescription of dulaglutide, and per subgroups.

Data coming from different databases/countries will not be pooled. The analysis will be done per year, and will not be cumulative. Thus data coming from different years will not be pooled either.

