Glucagon-like peptide-1 receptor agonists (GLP -1 RAs) are incretin mimetics. Similar to endogenous hormone GLP-1 (1), they inhibit glucagon secretion, delay gastric emptying and suppress appetite. They stimulate insulin secretion in a glucose-dependent manner; insulin release stops when the plasma glucose level is low (3 mmol/l) (2). The GLP-1 RAs are widely used as glucose-lowering drugs in the treatment of T2DM (3).

Five GLP-1 RAs are currently approved worldwide for treatment of adults with T2DM: exenatide (2 forms with daily/weekly administration: Byetta® was approved by the EMA in November 2006 / Bydureon® in 2011, Astra Zeneca), liraglutide in July 2009 (Victoza®, Novo Nordisk), lixisenatide in February 2013 (Lyxumia®, Sanofi), albiglutide in March 2014 (Eperzan®, GlaxoSmithKline) and dulaglutide in November 2014 (Trulicity®, Eli Lilly and Company). Currently all are marketed in Europe. Additionally, one formulation which comprises insulin Degludec and liraglutide, IDegLira (Xultophy®, Novo Nordisk) as single-device combination therapy was approved in September 2014.

Dulaglutide is a long-acting GLP-1 RA. Its structure protects it from inactivation by dipeptidyl peptidase-4 (DPP-4) and confers a half-life up to ~4.7 days in humans (4). As a result of this relatively long half-life, dulaglutide can be administered once weekly which may offer an advantage compared to some competitors, such as short acting exenatide which is given twice daily, and liraglutide or lixisenatide which are used once daily. It is to be noticed that as dulaglutide, long-lasting exenatide (Bydureon®), and albiglutide (Eperzan®) are also used once weekly.

The European Union (EU) Commission approved the dulaglutide injectable solution for the treatment of T2DM in November 2014 (5).

As part of the risk management plan (RMP), Eli Lilly, the Marketing Authorisation Holder (MAH) of dulaglutide has agreed to conduct a DUS to describe the use of dulaglutide in particular subgroups of patients in several databases in European countries.

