9.3. Variables

Regardless of the coding system used in the database, different populations and subgroups of interest are defined as follows:

Treatment initiation with dulaglutide:

- any record of prescription of dulaglutide during the observation period without prior record of prescription of the same product in the available patient's history
- if no prior history is available to check the above criteria, the prescription is not considered as an initiation

Patients presenting with T2DM:

- with any recorded diagnosis code for T2DM
- or with any recorded treatment code for an ADM other than insulin
- or, with any recorded treatment code for insulin initiated at age >30 (defined as no record of insulin therapy during 6 months prior to first record of insulin treatment)
- or with any record of unspecified diabetes mellitus diagnosis at age >30 and without history of insulin therapy (defined as no record of insulin therapy during 6 months prior to first record of diabetes diagnosis),
- a sensitivity analysis will be conducted to determine the age threshold mentioned above (see section 9.7.3 Sensitivity analysis).

Patients with severe renal failure:

- with a recorded diagnosis of severe renal failure
- or with a recorded glomerular filtration rate (eGFR) value <30 ml/min/1.73 m²

Patients with hepatic disease:

- with a recorded diagnosis of any hepatic disorder

Patients with heart failure:

- with a recorded diagnosis of heart failure

Patients with severe gastrointestinal disease:

- with a recorded diagnosis of any of the following conditions:
 - cancer of the gastrointestinal tract,
 - diseases of the oesophagus,
 - active ulcer at the time of drug initiation (gastric, duodenal, gastro-jejunal, peptic ulcer of unspecified site),
 - active haemorrhagic gastritis, chronic atrophic gastritis, adult hypertrophic pyloric stenosis, obstruction of duodenum, and other motility disorders,
 - digestive fistula,
 - Crohn's disease, ulcerative colitis,
 - diverticular disease of the intestine,
 - severe vomiting, severe diarrhoea and severe constipation
 - motility disorders, including ileus, gastroparesis, et cetera,
 - infectious and inflammatory situations (appendicitis, cholecystitis, cholangitis).

Children and adolescents:

- Age < 18 at the time of treatment initiation
(subgroups of analysis: 0-4, 5-9, 10-14, and 15-17 years old).

Elderly:

- Age \geq 75 at the time of treatment initiation.

Pregnant and breastfeeding women:

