9.7.4. Data Tabulation

The following outcomes/measurements of interest will be analysed:

- Patients' demographics (age and gender) at baseline
- Relevant comorbidities
- Medical history: disease diagnoses (using appropriate disease classification)
- Concomitant ADMs
- Other drug exposures (main therapeutic classes)
- Average daily dosage of prescriptions
- Prescriptions in combination with other ADMs

These characteristics will be described for overall patients initiated with dulaglutide and in the subgroups of interest corresponding to dulaglutide initiators. Some characteristics of dulaglutide initiators will be described at both the index date and the baseline period, for example, concomitant medications will be defined as those prescriptions recorded at the index date of dulaglutide initiation, while medication history will be defined as those medications which were recorded during the 6-month baseline period prior to dulaglutide initiation.

Note that subgroups will not be mutually exclusive: a patient could be part of more than one subgroup (for example, elderly patients ≥ 75 years and with hepatic disease). The column 'All' in [Table 9.7.4-1](#) will include the results corresponding to the overall data set and not the sum of the results of each subgroup. It also includes patients who are not categorised in any of the subgroups.

Table 9.7.4-1. Mock Table for the Description of the Use of Dulaglutide - Primary Objective: Description of the Use of Dulaglutide per Subgroups

Dulaglutide Country: Sweden	Subgroups of interest				
	1. Patients with severe renal failure (N=xx)	2. Patients with hepatic disease (N=xx)	...	9. Patients with off-label use (N=xx)	10. All (N=xx)
Outcomes/Measurements of interest					
Age (ranges)					
Missing					
< 18 years	xx (xx.x%)	xx (xx.x%)		xx (xx.x%)	xx (xx.x%)
0-4	xx (xx.x%)	xx (xx.x%)		xx (xx.x%)	xx (xx.x%)
5-9	xx (xx.x%)	xx (xx.x%)		xx (xx.x%)	xx (xx.x%)
10-14	xx (xx.x%)	xx (xx.x%)		xx (xx.x%)	xx (xx.x%)
15-17	xx (xx.x%)	xx (xx.x%)		xx (xx.x%)	xx (xx.x%)
18-44 years	xx (xx.x%)	xx (xx.x%)		xx (xx.x%)	xx (xx.x%)
45-64 years	xx (xx.x%)	xx (xx.x%)		xx (xx.x%)	xx (xx.x%)
65-74 years	xx (xx.x%)	xx (xx.x%)		xx (xx.x%)	xx (xx.x%)
≥75 years	xx (xx.x%)	xx (xx.x%)		xx (xx.x%)	xx (xx.x%)
Mean (SD)					
Min-Max					
Median [Q1- Q3]					
Gender					
Missing	xx (xx.x%)	xx (xx.x%)		xx (xx.x%)	xx (xx.x%)
Male	xx (xx.x%)	xx (xx.x%)		xx (xx.x%)	xx (xx.x%)
Female	xx (xx.x%)	xx (xx.x%)		xx (xx.x%)	xx (xx.x%)
Medical history					

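### The first-line off-label count tests only the six-month baseline, so it takes in index-date combination starters and earlier ADM users; age under 18 is not itself an off-label criterion

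*Protocol*

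**What the plan says.** Protocol Section 9.3 gives two off-label criteria. The first is "Prescribed dulaglutide with no diagnosis of T2DM as defined above". The second applies to patients who do have T2DM and were prescribed dulaglutide "without a record of other ADMs during the 6-month baseline period, i.e. dulaglutide was prescribed as first-line therapy". Table 9.3.2-1 repeats both; neither place mentions age.

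The abstract (Section 4, Variables) names two separate time points: "baseline (6-month period prior to dulaglutide initiation) and/or index date (dulaglutide initiation"). Section 9.7.4 keeps them apart for drugs: "concomitant medications will be defined as those prescriptions recorded at the index date of dulaglutide initiation", whereas medication history means "those medications which were recorded during the 6-month baseline period prior to dulaglutide initiation".

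The T2DM definition in Section 9.3 has no such window. One of its routes is "or with any recorded treatment code for an ADM other than insulin".

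Section 9.9.1 explains that appropriate and inappropriate monotherapy cannot be told apart, and concludes that "the number of patients found to be taking off-label first line dulaglutide will be an overestimate".

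On the approved population, Section 7 says: "Five GLP-1 RAs are currently approved worldwide for treatment of adults with T2DM", and lists dulaglutide among the five. Section 8 makes off-label use within each population of interest, under-18s included, the secondary objective.

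**The concern.** The second criterion is named first-line in Section 9.3 and explained as monotherapy in Section 9.9.1, but what it measures is the absence of another ADM in one six-month window. Two groups meet it without fitting the monotherapy description, or without plainly being first-line:

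- patients given another ADM on the index date, who are not on monotherapy;
- patients treated with another ADM earlier, whose records stop more than six months before index.

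The age question is separate. If the approval is for adults, as Section 7 puts it, a patient under 18 with T2DM and a recent ADM is outside it, yet the rule reports that patient as not off-label.

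Off-label use is a subgroup in the primary objective and the whole of the secondary objective. The protocol itself fixes the definition, so this is not a detail left to the SAP.

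**Working it through.** **Plan's own figure.** The protocol states no expected off-label proportion, so there is none to reproduce. Its only computed figures, the precision sample sizes in Section 9.5.1 (384, 1066 and 97), do not bear on this point.

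**Applying the rule.** Take five yes/no attributes: age under 18; a T2DM diagnosis code; another ADM more than six months before index; another ADM in baseline; another ADM on the index date. That gives 2^5 = 32 patterns. The other ADM is taken to be non-insulin, so any record of it establishes T2DM. The two criteria of Section 9.3 then give:

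| Patterns | Number | Counted off-label |
|---|---|---|
| No baseline ADM | 16 | 16 |
| – of which ADM on index date | 8 | 8 |
| – of which ADM only more than six months before index | 4 | 4 |
| – of which no other ADM at all | 4 | 4 |
| Baseline ADM | 16 | 0 |
| Under 18, any ADM pattern | 16 | 8 |
| Adult, any ADM pattern | 16 | 8 |

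These are counts of patterns, not patient shares. They show three things.

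1. Within this enumeration the flag depends only on whether there is a baseline ADM. Index-date and older ADMs never change it.
2. In the third group, the older ADM record can be the only thing that makes the patient T2DM, and it is then ignored when the patient is labelled first-line.
3. Under-18s are treated exactly like adults. Those without T2DM, or without a baseline ADM, are counted; those with T2DM and a baseline ADM are not.

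The T2DM text does not say whether dulaglutide's own code counts as a non-insulin ADM. Run both ways, the off-label total is the same; only the split between the two criteria moves.

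**Side by side with Section 9.9.1.** The admitted overestimate has one stated cause: appropriate monotherapy that cannot be recognised. A patient with an index-date ADM is not on monotherapy, so that cause does not cover the second row. Earlier ADM users are not mentioned either.

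**Size.** Let c be the share of initiators in the index-date group, e the share whose only ADM is older than six months, and u the share who are under 18 with T2DM and a baseline ADM. If c and e are regarded as wrongly counted and u as missed, the net error is c + e − u. The documents give none of the three. With assumed values:

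- c = e = 2%, u = 0.2% to 1%: +3.8 to +3.0 points
- c = e = 5%, u = 0.2% to 1%: +9.8 to +9.0 points
- c = e = 0, u = 0.2% to 1%: −0.2 to −1.0 points

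This shows only how the result moves with the assumptions.

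**The case against.** **A same-day starter with no earlier ADM is literally first-line.** This stands. The documents do not set out the combination indication, so they cannot settle whether that use is on-label. What remains is that Section 9.3 has no monotherapy condition and Section 9.9.1 reads the criterion as monotherapy.

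**Six months is the only history guaranteed for every patient** (Section 9.2.2), so it gives one uniform look-back. This also stands. The start years in Table 9.5.2-1 belong to databases, not to patients, and Section 9.9.1 says SIDIAP lacks diabetes history. An any-time rule would let the classification depend on length of record. A patient who stopped another ADM long ago and now takes dulaglutide alone is also on monotherapy, the very group Section 9.9.1 discusses.

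**The information is partly visible already.** The mock table has index-date ADM rows in every column and rows for T2DM treatment duration. But the off-label column pools both criteria, and in the population columns the first-line and index-date rows are separate margins. The joint count that the secondary objective needs is not shown.

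**Paediatric use is not hidden.** Under-18s have their own column and four age bands, and the sentences on dulaglutide's own EU approval mention T2DM without an age. This limits the consequence: the missed patients can be found. It does not remove the conflict between the adults wording in Section 7 and the off-label row in that column.

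**Stronger readings to avoid.** A reader might infer that under-18s are never counted, or that their off-label share would be near zero. The enumeration shows otherwise. A reader might also put a factor on the overstatement: if a fraction f of the first-line count were reclassified, the factor is 1/(1 − f), or 1.43 at f = 0.30 and 2.5 at f = 0.60. Those values of f have no source in the documents.

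**Conclusion.** The point holds in a limited form. The second off-label criterion combines three kinds of patient, only some of whom match the monotherapy concept in Section 9.9.1, and the limitation stated there does not cover index-date ADMs or older ADM use. Sections 9.3 and 9.9.1 must be reconciled. Age is not an off-label criterion, so under-18s with T2DM and a baseline ADM are reported as not off-label, against the description of the approval in Section 7; the downward error is confined to that group.

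The size, and hence the net direction, cannot be computed from the documents. The conclusion rests on reading baseline as excluding the index date, which the abstract and Section 9.7.4 support, and on taking the adults wording in Section 7 to apply to dulaglutide, which that sentence lists by name.

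**What to change.** Keep the six-month window as the main look-back. In Section 9.3, Table 9.3.2-1 and the mock table, split the first-line count:

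- (a) no other ADM in baseline or on the index date (monotherapy);
- (b) another ADM on the index date, none in baseline;
- (c) as a sensitivity row within (a), another ADM recorded only more than six months before index, with the median length of available history beside it.

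State that only (a) corresponds to the monotherapy concept of Section 9.9.1, and reword that limitation so that it covers (b) and (c). Show the split in every population column.

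Add age under 18 at initiation as a separate off-label category with its own row. Since a patient can meet more than one category, count each patient once in the total. Bring the approval wording in Section 7 and the off-label definition into agreement.

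Cost: wording and a few table rows. Index-date ADMs and age are already extracted. Row (c) needs records older than six months where they exist, and unequal history makes it less comparable between patients and countries, which is why it should stay a sensitivity row.
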